1.1. Clinical trials registration

This study is registered with clinicaltrials.gov: NCT02943109.

1.2 Ethics approval

The Institutional Review Board of The Ohio State University (OSU), College of Medicine (COM) approved the study.

1.3 Availability of data

The data used in this study includes identifiable information, and per our consent approval we are not permitted to share study data. However, the data management protocol and analytic approach will be made publicly available via publication.

1.4 Competing interests

The authors declare that they have no competing interests to report.

1.5 Funding

This work was supported by the Agency for Healthcare Research and Quality (AHRQ) Grants R01HS024091, R21HS024767, P30HS024379. While this research was funded by AHRQ, the study sponsor had no involvement in the collection, analysis, or interpretation of data, in the writing of this article, or in the decision to submit the article for publication.

1.8 Protocol revisions

Revision history of the protocol, including rationale, is provided in Table 1, sorted by date.

Table 1: Amendments to the study protocol (sorted by date).

Date	Revision	Rationale
Section reference		
February 2016	Low-Tech intervention: Changed from no tablet to Lite-Tech intervention with a tablet with a limited MyChart Bedside feature set.	Independent of the study, OSUWMC decided to implement MyChart Bedside system-wide, resulting in it not being possible to not provide some patients a tablet.
	Study site: Changed study sites from six matched unit pairs to OSUWMC system-wide, including six hospitals.	Independent of the study, OSUWMC decided to implement MyChart Bedside system-wide, resulting in it being feasible to expand the study sites across the OSUWMC.
February 2016	Focus on multiple chronic conditions: Changed from inclusion criteria of two or more chronic conditions to no disease restrictions.	Independent of the study, OSUWMC decided to implement MyChart Bedside system-wide, resulting in it being infeasible to restrict the sample based on disease characteristics.
	Inclusion criteria: Criteria of patient admitted within last 24 hours and expected discharge in more than 72 hours removed.	The expansion of the study from the six matched unit pairs to OSUWMC system-wide resulted in logistic challenges in being able to reaching all patients quickly. Additionally, OSUWMC does not store expected discharge in its Epic Clarity tables, making this criterion impossible to operationalize.
February 2016	Low-Touch intervention: Changed from active control where patients receive an in-person visit from a Technology Navigator (TN) to a passive control where patients were directed to self-guided learning materials built into MyChart Bedside.	Independent of the study, OSUWMC decided to implement MyChart Bedside system-wide. This change increased the number of potentially eligible patients for TNs to visit, presenting a logistical challenge. Additionally, in the original protocol where patients assigned to the Low-

Section 3.1		
Tech arm did not receive a tablet, it was not possible to deliver a passive control. However, when the protocol changed to all study participants receiving a Tablet (Full/Lite-Tech), a passive control arm was possible. This approach resolved the logistical challenges.

December 2016	
Hypotheses: The primary and secondary hypotheses were revised and reduced from seven to four hypotheses.
	
In the original proposed study, the plan was to execute it using 12 units and limit the study to chronic diseases. Additionally, participants were to be randomized to receive no technology or a full version of the MyChart Bedside application on the tablet. OSUWMC made several decisions that had an effect on the study design. In particular, OSUWMC determined that not providing a tablet was no longer an option; however, they made the units across the entire hospital system available for the study. The research team worked with OSUWMC to refine the hypotheses needed to reflect the more inclusive study. This resulted in dropping readmissions and comfort with technology as outcomes of interest, among other revisions.

Section 2.2		
July 2017	
Improve enrollment yield: A research team member may visit the patient to remind them to complete the survey, limited to three visits per patient, once per day. Patients without completed surveys could also be visited on subsequent hospital admissions to complete their survey.
	
Quality assurance testing of the data collection system identified a technical problem which caused an unusual pattern of missing responses. Inspection of completeness of questions identified a pattern of non-completion such that every 5-10 questions, a question would demonstrate a considerably lower percent missing than the questions asked immediately before and after it. This pattern was attributed to the display of the survey on Qualtrics that hid some questions from view. A reminder was added to the survey to inform respondents if they had left questions unanswered as they clicked the button to advance

Section 4.2.1		

		the survey, still allowing them to advance if that was their preference.
July 2017	Study enrollment: A confirmation was added to each page of the survey to inform respondents when they had left questions unanswered on a page. They could continue to advance if that was their preference.	Completion of the survey was found to limit the number of patients in the High-Touch study arm. This change represented a deviation from the original protocol which had required that the Admission survey be completed prior to intervention delivery.
February 2018	Study allocation: The allocation of individuals in arms were rebalanced to ensure sufficient numbers of participants in the High-Touch treatment arm due to a significant number of patients becoming lost to follow-up.	Quality monitoring of the study found a number of exogenous factors that were impacting the High-Touch intervention, including, but not limited to: patient discharges; patient moves to other rooms; patients not present during rounding; patients' engagement with the care team; and tablet returns prior to receiving an intervention. This change was done to ensure that sufficient individuals were assigned to the High-Touch intervention to increase the number of patients who would be eligible to receive a High-Touch intervention.
Section 3.1.3	Intervention available after consent: TNs are allowed to make first contact for the High Touch intervention once the patient consented – no longer waiting for a complete Admission Survey. The TN should work with the patient to walk them through completing the survey during the intervention.	As noted in Section 3.1.3 changes were made to the intervention protocol to facilitate greater engagement in the High-Touch arm. Specifically, prior to February 2018, participants assigned to the High-Touch intervention group did not receive the intervention until after they had completed the Admission survey. Starting on February 22, 2018, the research team modified the protocol to allow TNs to mark a survey as complete and allow the intervention team to perform the High-Touch intervention. In March 2018, 22 days later, the protocol was once again changed to deliver the High-Touch intervention at first contact with the TN if they had been assigned to the High-Touch intervention.
Section 4.2.1		

July 2018	
Intervention assignment: Individuals that had activated a MyChart Bedside account prior to the study start or in a Full-Tech unit were manually assigned to the Full-Tech intervention regardless of their MRN. Individuals who were found to have accessed both Full and Lite versions over the course of the study were excluded from the analysis for this study.
	
Quality assurance testing of ongoing data collection of the MyChart Bedside usage data revealed that patients who were to have been assigned to Lite-Tech based on their MRN were, in fact, using functions only available on Full-Tech. Subsequent review also found the reverse to be true, participants that were assigned to Full-Tech were limiting their usage to those functions in Lite-Tech.
 
The study team conferred with Epic—the electronic health record (EHR) vendor that developed the code to assign patients to a particular arm of Tech status—and manually reconstructed Tech assignment using the original assignment code. A cohort of individuals were identified as not having received the intended Tech assignment. Through this process, the study team was able to secure the true Tech intervention status. Individuals that had activated a MyChart Bedside account or were in a Full-Tech unit prior to the study start were manually assigned to Full-Tech regardless of their MRN. Additionally, individuals who were found to have accessed both Full and Lite versions over the course of the study were identified and subsequently excluded from the analysis for this study. This scenario may have occurred when a patient was assigned an MRN at admission but subsequent records review identified an existing MRN. In these cases, individuals unexpectedly transitioned between two Tech intervention states.

Section 4.2.1		

Section 2: Introduction

2.1 Background and rationale

For patients with complex care needs, engagement in disease management activities is particularly critical.¹⁻⁴ The human cost of chronic illnesses touches almost every person in the US. These costs are real, personal and pervasive.⁵ In response, patients often seek out tools to help them manage their health. Patient portals—a Personal Health Record (PHR) tethered to an Electronic Health Record (EHR)—show promise as tools that patients accept and value and that can improve health.⁶⁻¹⁰ Although patient portals currently focus on the outpatient experience, the Ohio State University Wexner Medical Center (OSUWMC) has deployed a portal designed specifically for the inpatient experience that is connected to the ambulatory patient portal available after discharge. While this inpatient technology is in active use at only one other hospital in the US, healthcare facilities are currently investing in the infrastructure necessary to support large-scale deployment.¹¹

Times of acute crisis such as hospitalization may increase a patient's focus on his/her health, a factor that has been linked in other areas to a greater awareness of health risks and increased focus on health behaviors.¹²⁻¹⁴ During this time, patients may be more engaged with their care and therefore particularly interested in the potential for using tools to manage their health after discharge. Evidence shows that enhanced patient self-management can lead to better control of chronic illness,^{1,15,16} and patient portals may serve as a mechanism to facilitate increased engagement.¹⁷⁻¹⁹

Our proposed four-year study used a mixed-methods approach to evaluate a pragmatic randomized controlled trial (RCT) studying the effectiveness of a High-Tech Intervention (MyChart Bedside, the inpatient portal), and an accompanying High-Touch Intervention (training patients to use the portal to manage their care and conditions) in a sample of hospitalized patients. This study measured how a patient portal tailored to the inpatient stay could improve patient experience and increase patient engagement by 1) improving patients' perceptions of the process of care while in the hospital, 2) increasing patients' self-efficacy for managing their health and health care, and 3) facilitating continued use of a patient portal for care management activities after discharge. In addition, we aimed to enhance patients' use of the patient portal available to outpatients, MyChart, once they were discharged.

2.2 Objectives

The ***High Tech and High Touch (HT2): Transforming patient engagement throughout the continuum of care by engaging patients with portal technology at the bedside*** study at OSU Wexner Medical Center (OSUWMC) sought to study how the deployment of a commercial (i.e., Epic Systems) inpatient portal, MyChart Bedside, impacted identified patient outcomes. To evaluate the impact of function set and training

on inpatient (i.e., MyChart Bedside) and outpatient (i.e., MyChart) portal use, the HT2 Study²⁰ was designed as a large-scale, pragmatic randomized controlled trial across six hospitals in a healthcare system.

Using a two-by-two factorial design, HT2 simultaneously examined the effects of two approaches to portal training with two versions of the inpatient portal. HT2 was designed to test four study hypotheses:

Hypotheses related to primary outcomes:

H1: Patients assigned to the High intervention levels for Tech and Touch will demonstrate higher use of MyChart Bedside.

H2: Patients assigned to the High intervention levels for Tech and Touch will demonstrate higher levels of satisfaction with (H2a) and involvement in (H2b) their care experience.

Hypotheses related to secondary outcomes:

H3: Patients assigned to the High intervention levels for Tech and Touch will demonstrate higher rates of outpatient portal adoption (i.e., of Epic's MyChart) for those admitted without prior outpatient portal use (H3a), and higher use of MyChart for those admitted who had previously used the outpatient portal (H3b).

H4: Patients assigned to the High intervention levels for Tech and Touch will demonstrate higher levels of self-efficacy.

To prevent outcome reporting bias and data-driven analysis of results, we produced this detailed statistical analysis plan. The plan was originally developed and drafted prior to examination of the data, and in the absence of randomization knowledge. The plan has been revised as the analysis has proceeded.

Section 3: Study methods

3.1 Trial design

This study was designed as a pragmatic factorial randomized controlled trial of two concurrent patient portal-related interventions.

3.1.1 Intervention description: Tech - Full/Lite

The Full-Tech intervention consisted of the standard build of the MyChart Bedside product as delivered from Epic and augmented by OSUWMC at the start of the study. The application was served by a *Home* landing page that displays events scheduled for the day and recent health updates and included access to 10 additional functions located in tabs along the side of the inpatient portal image:

1. *Home*: presented events scheduled for the day and data on patient vitals, including last blood pressure reading, current pulse and other patient vital signs refreshed from the Electronic Health Record (EHR) once every 5 minutesⁱ
2. *Bedside Tutorial*: tutorial materials for the use of MyChart Bedside, including an 11-minute video explaining how to use MyChart Bedside and access to PDF versions of tutorial materials
3. *Dining on Demand*: food ordering service
4. *To Learn*: educational resources for the patient based on their treatment plan
5. *Happening Soon*: a timeline for the care activities that the patient could expect for the day
6. *Taking Care of Me*: information detailing members of the patient's care team
7. *Messages*: non-urgent secure messaging with the patient's care team
8. *My Health*: recent vital signs and lab test results
9. *Notes*: write/record reminders and notes
10. *I Would Like*: non-urgent requests from pastoral care or gift shop
11. *OSU MyChart*: allowed the patient to access MyChart, including creating a new account

In addition to the *Home* landing page, the Lite-Tech version of MyChart Bedside consisted of the 3 functions: *Bedside Tutorial*, *Dining on Demand*, and *To Learn*.

3.1.2 Intervention description: Touch - High/Low

The education and training intervention, referred to as Touch, was performed by trained Technology Navigators (TNs) who deliver training tailored to both the version of

ⁱ This function was automatic, so was not considered selectable and not included in the count of functions for either the Full- or Lite-Tech versions.

MyChart Bedside installed on their tablet (both Full- and Lite-Tech) and the perceived capacity of the patient.

Patients assigned to the Low-Touch intervention received an intervention focused on providing them with resources to conduct self-guided learning of MyChart Bedside. Specifically, TNs directed patients to the tutorial videos integrated in the MyChart Bedside application that explained the portal's functions.

In contrast, patients assigned to the High-Touch intervention would systematically review each of the functions of MyChart Bedside with the TN who would discuss how and when they are appropriately used. Patients were encouraged to use their tablet and follow along with the training as the TN moved through each function and ask the TN questions about their records during the presentation. The TNs tailored their presentation based on a patient's demonstrated knowledge of the technology to minimize patient participation burden while focusing on explaining the value of each function within the application. Patients unavailable after three intervention attempts were converted to Low-Touch.

3.1.3 Allocation ratio

The Tech intervention contrasted two function sets—Lite-Tech (40% allocation), which was a minimalistic toolset focused on providing basic data to the patient, and Full-Tech (60% allocation), a more expansive toolset. The Touch intervention contrasted two training approaches—Low-Touch, a self-guided approach where patients could view built-in tutorials, and High-Touch (initially 50% allocation), where patients receive in-person guided training with the technology. The realized allocation ratios are presented in Table 2.

Table 2. Realized allocation ratio.

Tech Allocation	Touch Allocation		Total
	High	Low	
Full			
Frequency	624	1,523	2,147
Row %	29.1%	70.9%	100.0%
Column %	69.3%	76.5%	74.2%
Overall %	21.6%	52.7%	74.2%
Lite			
Frequency	277	468	745
Row %	37.2%	62.8%	100.0%
Column %	30.7%	23.5%	25.8%
Overall %	9.6%	16.2%	25.8%
Total			
Frequency	901	1,991	2,892
Row %	31.2%	68.8%	100.0%
Column %	100.0%	100.0%	100.0%
Overall %	31.1%	68.8%	100.0%

The assignment protocol used three phases where the Touch allocation ratio was changed by the research team.

1. In Phase 1, patients received the High-Touch intervention only after consenting to the study and submitting their Admission survey (see Section 3.8.2). Low-Touch patients could view the tutorial at any point and were not required to complete the Admission survey. Phase 1 assigned patients to High/Low-Touch in a 1:1 ratio.
2. In Phase 2, beginning in February 2018, the study shifted to a 3:1 ratio of High/Low-Touch. This change was done to ensure that sufficient individuals were assigned to the High-Touch intervention due to under-enrollment. Quality monitoring of the study found a number of exogenous factors that were impacting the High-Touch intervention, including, but not limited to: patient discharges; patient moved to other rooms; patient not present during TN rounding; patient was engaged with the care team and unable to work with the TN; and tablet returned prior to receiving an intervention. This change in the ratio was intended to increase the number of patients who would be eligible to receive a High-Touch intervention while maintaining the *per protocol* approach in that these exceptions were considered a component of the Protocol.
3. Phase 3 began in March 2018 and lasted through the end of the study in September, 2018. This phase maintained the 3:1 split, but removed the requirement that patients complete the Admission survey prior to receiving the High-Touch intervention. Completion of the survey was found to limit the number of patients in the High-Touch study arm. This change represented a deviation

from the original protocol which had required that the Admission survey be completed prior to intervention delivery (see Section 4.2.1).

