4.2.1 Operational protocol amendments

Operational protocol amendment 1: Improve enrollment yield (Jan 2017)

A research team member could visit the patient to remind them to complete the survey, limited to three visits per patient, once per day. Patients without completed surveys could also be visited on subsequent hospital admissions to complete their survey.

Operational protocol amendment 2: Improve data quality (Jul 2017)

A confirmation was added to each page of the survey to inform respondents when they had left questions unanswered on a page. They could continue to advance if that was their preference.

Operational protocol amendment 3: Intervention available after consent (Feb 2018)

TNs were allowed to make first contact for the High-Touch intervention once the patient consented—no longer waiting for a complete Admission survey. The TN should work with the patient to walk them through completing the survey during the intervention.

Operational protocol amendment 4: Intervention assignment (Mar 2018)

Individuals that had activated a MyChart Bedside account or were in a Full-Tech unit prior to the study start were manually assigned Full-Tech regardless of their MRN.

Individuals who were found to have accessed both Full and Lite versions over the course of the study were to be excluded from the analysis for this study.

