4.3 Analysis populations

The analytic population of the study used a *per protocol* approach. Using this paradigm, study participants assigned to the High-Touch group that did not receive the High-Touch intervention were reassigned to the Low-Touch group. In rare instances (n=3) where a patient was assigned to the Low-Touch group but received the training intervention due to patient request, they were reassigned to the High-Touch group.

Section 5: Trial population

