### 1.4 Assumptions and testing

#### 1.4.1 Analysis populations

Estimates of the intervention effects were calculated on two analytic populations. The main analytic population of the study used an *intention-to-treat (ITT)* approach. Using this paradigm, participants were analyzed on the basis of the study group to which they were randomized, regardless of their eventual receipt of that intervention.

The effects of the intervention were additionally evaluated on a *per-protocol* population, composed exclusively by those participants who were administered their randomized intervention. The analysis of the data from the per-protocol population was weighted by the inverse of their probability to receive the intervention to which they were originally randomized, computed on the basis of the following demographic and clinical characteristics: sex, race, age at time of enrollment, Charlson Comorbidity Index, length of stay.

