#### 1.4.2 Analytic framework

A review of factorial randomized control trials identified that the appropriate analytics model, in general, would adhere to Equation 1 (see below), assuming that the basic functional form for regression is the appropriate approach. This approach was used per Montgomery et al. Variations to this functional form are noted below.

$$\text{Eq. 1: } y = X_{Tech} + X_{Touch} + X_{Tech*Touch}$$

To address potential differences in variance associated with the multi-site and pragmatic aspects of the study (e.g., expansion of the study after it was originally conceptualized and operationalized, differences in policies and procedures across hospitals and units), we performed cluster-robust standard errors in the estimation of the outcomes. The analysis clusters study participants by the hospital where the study participant was enrolled. To validate this assumption, a sensitivity analysis was performed on patients transferred to different hospitals within the medical center.

Further, to account for heterogeneity in duration of patient access to the inpatient portal, we included the length of tablet provisioning, measured in days, as an offset parameter in all models.

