#### 1.5.1 Outcome 1 – Number of MyChart Bedside sessions within the enrollment admission was dependent on treatment

*Dependent variable specification:* The count of MyChart Bedside sessions for the admission associated with study enrollment.

- Enrollment admission was defined as the admission when the patient was enrolled in the study.

*Statistical model:* Negative binomial model with non-interacted and interacted study arms as binomial predictors.

---

ii Preliminary analysis of adoption rates for the outpatient portal revealed a rapid decrease in the numbers following the first few months, which motivated us to set the value for the cutoff date at 90 days in order to more conservatively attribute portal use to an individual's participation in the study.

*Covariates:* No covariates were added to this analysis.

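### Touch was randomised 1:1 and then 3:1 from February 2018, but no model or weight contains phase, so the pooled Touch effect may be partly confounded with period

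*Protocol*

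**What the plan says.** **Allocation.** Protocol section 3.1.3 assigns Touch 1:1 in Phase 1. Then: "In Phase 2, beginning in February 2018, the study shifted to a 3:1 ratio of High/Low-Touch". Phase 3 runs from March to September 2018: "This phase maintained the 3:1 split, but removed the requirement that patients complete the Admission survey prior to receiving the High-Touch intervention".

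**Delivery.** The survey condition for High-Touch was relaxed in stages. Section 1.8: "Starting on February 22, 2018, the research team modified the protocol to allow TNs to mark a survey as complete". It then reports a further change in March 2018, 22 days later. Amendment 3 in section 4.2.1: "TNs were allowed to make first contact for the High-Touch intervention once the patient consented".

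**Models.** Equation 1 (SAP 1.4.2) has Tech, Touch and their product. All models also carry tablet provision length as an offset. On standard errors: "The analysis clusters study participants by the hospital where the study participant was enrolled". Most outcome sections repeat the statement in SAP 1.5.1: "No covariates were added to this analysis". The exceptions are an Admission survey item for satisfaction (SAP 1.6.1) and pre-enrolment sessions for prior MyChart users (SAP 1.7.5).

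**Populations.** SAP 1.4.1 makes ITT the main analysis. The per-protocol weights are built from "sex, race, age at time of enrollment, Charlson Comorbidity Index, length of stay". Protocol section 4.3 instead describes moving patients by receipt: "study participants assigned to the High-Touch group that did not receive the High-Touch intervention were reassigned to the Low-Touch group".

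**The concern.** When the allocation ratio changes during a trial, randomisation is valid within each phase but not across the pooled sample. Pooling without a phase term makes arm and calendar period correlated, so an outcome that differs between Phase 1 and Phases 2-3 for any reason shifts the Touch estimate, in either direction. Phases 2 and 3 share one ratio, so a difference between those two does not bias the ITT estimate.

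Touch is one of the two randomised factors and enters H1 to H4. The baseline covariates in SAP 1.6.1 and 1.7.5 may absorb part of a period difference. The H1, involvement, H3a and H4 models have no covariate that could.

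The staged change in delivery is a separate matter. It alters who receives High-Touch and what the treatment was. That is not ITT confounding, but it makes receipt depend on phase, and the per-protocol weights ignore it.

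**Working it through.** The documents give no figure for this bias to reproduce, and no enrolment or outcomes by phase. What follows is an illustration for the arms as randomised.

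**Inputs from the documents.** P(High) = 0.50 in Phase 1 and 0.75 afterwards (Protocol 3.1.3); total n = 2,892 (Protocol Table 2); significance level 0.05 (SAP 1.1), taken as two-sided.

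**Assumed.** Share enrolled under 3:1, f = 20-60%; period difference D = 2, 5 or 10 points; base rate p = 30-50%; independent patients; no true Touch effect; and n = 1,000 as an alternative for survey or subgroup outcomes.

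**Why only the total is taken from Table 2.** Ratios of 1:1 and then 3:1 imply between 50% and 75% High. Table 2 shows 901/2,892 = 31.2%, which is 1,446 − 901 = 545 fewer than half. It cannot be the randomised split, and it fits the reassignment in Protocol 4.3.

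**Step 1: share of a period difference that passes through.**

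- Overall High share: H = 0.5 + 0.25f
- P(late | High) = 0.75f / H
- P(late | Low) = 0.25f / (1 − H)
- Pass-through g = P(late | High) − P(late | Low)

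At f = 0.4: H = 0.60, so g = 0.30/0.60 − 0.10/0.40 = 0.50 − 0.25 = 0.25.

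| f | P(late given High) | P(late given Low) | g |
|---|---|---|---|
| 0.1 | 0.143 | 0.053 | 0.090 |
| 0.2 | 0.273 | 0.111 | 0.162 |
| 0.3 | 0.391 | 0.176 | 0.215 |
| 0.4 | 0.500 | 0.250 | 0.250 |
| 0.5 | 0.600 | 0.333 | 0.267 |
| 0.6 | 0.692 | 0.429 | 0.264 |
| 0.8 | 0.857 | 0.667 | 0.190 |

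The maximum is 0.268, near f = 0.54.

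**Step 2: bias and type I error.**

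- Bias = g × D
- SE = √[p(1−p)(1/nH + 1/nL)], with nH = nH-share × n at H and nL at 1 − H
- Type I error = Φ(−1.96 + s) + Φ(−1.96 − s), where s = bias/SE

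At f = 0.4, D = 10 points, p = 0.5, n = 2,892: nH ≈ 1,735 and nL ≈ 1,157; SE = 1.90 points; bias = 2.5 points; s = 1.32; type I error = 26.1%.

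Over f = 20-60% and p = 30-50%:

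| D | Bias (points) | Type I error, n = 2,892 | Type I error, n = 1,000 |
|---|---|---|---|
| 2 points | 0.3-0.5 | 5.3-6.1% | 5.1-5.4% |
| 5 points | 0.8-1.3 | 7-12% | 6-7% |
| 10 points | 1.6-2.7 | 14-33% | 8-15% |

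For scale, Protocol 3.4 says the design was meant to detect changes of 2.2% to 3.8% in satisfaction scores.

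**Step 3: does a phase term repair it?** Two simulations with no true Touch effect say yes.

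- Linear model: 4,000 runs per setting, D = 10 points, n = 2,892. Type I error is 14-32% without phase; with phase it is 4.3-5.1% and the bias is 0.0 points.
- Logistic model: 1,000 runs per setting, D = 5 or 10 points, p = 0.5. At f = 0.5 and D = 10, type I error is 25.8% without phase and 5.1% with it. Across all settings with phase it is 4.3-5.5%.

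**Step 4: cost in precision.** Information lost = 1 − [0.25(1−f) + 0.1875f] / [H(1−H)]. At f = 0.4 this is 1 − 0.225/0.240 = 6.3%. Over f = 20-60% it is 4.0-6.7%.

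**Per-protocol analysis.** Its bias cannot be sized, because delivery of High-Touch by phase is not given.

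**The case against.** The structural facts are not in dispute, but four objections deserve weight.

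- **No drift has been shown, and the large figures need a large one.** This stands as a limit on size. If the period difference were only 2.2 to 3.8 points, borrowing the detectable changes in Protocol 3.4, the same formulas give 0.36-1.01 points of bias and a type I error of 5.4-8.9% at n = 2,892, or 5.1-6.3% at n = 1,000. Those detectable changes do not bound the actual drift, however.
- **The provision-length offset is in every model.** It could remove a period difference that acts through time with the tablet, most plausibly for the H1 session count. It is not a phase term and does not restore balance within the randomisation strata. Hospital clustering changes standard errors, not the estimate.
- **The sizing is not for the planned models.** It uses risk differences and independent patients, whereas the SAP has negative binomial and linear models and clustered errors. The type I figures therefore do not carry over directly. The pass-through share for an additive difference does not depend on the standard errors.
- **The analysed arms may not be the randomised ones.** Protocol 4.3 and SAP 1.4.1 disagree. If reassigned arms were used, the link between arm and phase also depends on delivery by phase, and these figures do not apply.

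**Conclusion.** The concern holds. The omission is certain: the Touch ratio changed, and no model, weight or sensitivity analysis conditions on phase. The harm is conditional on an outcome difference between the 1:1 and 3:1 periods. At most about 27% of an additive difference reaches the ITT Touch estimate, which is close to harmless for a 2-point difference and serious for a 10-point one. These sizes rest on an assumed enrolment split, assumed period differences and base rates, independent patients, and arms as randomised. The actual size and direction cannot be known until enrolment and outcomes are shown by phase. The change should be made because it removes a possible bias at little cost.

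**What to change.** 1. Add randomisation phase, at least 1:1 versus 3:1, as a factor in every H1-H4 ITT model, including the Full-Tech sub-sample (Equation 2), and in the per-protocol weight model.
2. Report enrolment by phase and randomised Touch arm, before any reassignment by receipt.
3. Show Touch estimates by phase or a Touch-by-phase term, because a main effect does not cover the change in High-Touch delivery. Phase 2 may have lasted only about 22 days, so a separate estimate for it may say little; state how phases are pooled.
4. The SAP describes the analyses as done, so label this a post-hoc sensitivity analysis and state whether any Touch conclusion changes.

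**Cost.** A re-run and one table; one or two extra parameters for the main effect, with about 4-7% less information on Touch. Phase-specific estimates will be less precise. No new data collection is needed: consent ran in Qualtrics, as did most Touch randomisation, so phase can be derived from enrolment dates. The team must supply the exact day of the switch, since section 3.1.3 gives only the month, and must date the patients assigned from the separate randomisation table (Protocol 3.2.2).
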